**7.1.14. Unscheduled Visits at subject's local site or at Stanford**

Unscheduled exams may be conducted at the discretion of the Investigator with all obtained information recorded in the source documents. Subjects will be requested to have their local physician also send us any information on visits they may have with their local physician related to the lymphatic malformation or lymphatic malformation treatment.

**7.1.15. Concomitant Medications**

A concomitant medication is any drug or substance administered from the signing of the informed consent for the study through the last study visit Items 3 and 4 in Section 5.3 (Exclusion Criteria) list those medications that are not permitted during the study period. Investigational drugs or devices: The use of concomitant therapies must be documented in the subject's source documents.

**7.2. DISCONTINUED SUBJECTS**

Discontinued subjects are those who voluntarily discontinue participation, who are withdrawn for safety reasons or use of prohibited concomitant treatments, or who have missed a sufficient number of study visits, procedures or test medication doses as to be ineligible for further participation.

All subjects who discontinue the study prior to completing the regularly scheduled visits must complete the EOT and Exit Visit procedures described in Section 7.1.11. Any changes in medical health and/or the use of concomitant treatments must be captured. If any adverse events were observed since the previous visit, they must be recorded

(refer to Section 13, Adverse Events). Finally, if appropriate, the Investigator also should advise the subject's parent or legally authorized representative of subsequent therapy and/or procedures necessary for their medical condition.

In the case of subjects who persistently fail to return for scheduled visits, three attempts must be made to contact the subject's parent or legally authorized representative for the purpose of scheduling an Exit/EOS Visit. The third attempt should be via registered mail, return receipt requested.

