## 6.2. METHODS USED TO MINIMIZE BIAS

All subjects will have the option to receive 20 weeks of sildenafil in this open label extension study design. Subject assignment to sildenafil or placebo in the initial treatment period will be random.

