**7.1.13. Early Exit at subject's cooperating research site or at Stanford**

In addition to the procedures required at the EOT visit:

1. The subject will be exited from the study.
2. Study medication will be collected. The subject may elect to not return to Stanford or the cooperating research site for this visit. In this case, we will have them mail the unused medication back to Stanford. We will give them pre-addressed shipping forms. If the subject does not return for this visit, we may also arrange to get the pregnancy test at a local hospital or local office.

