## **10. STATISTICAL DESIGN**

### **10.1. EVALUABILITY**

All subjects who receive study medication will be evaluable for the safety analysis. All subjects who receive study medication will be evaluable for the intent-to-treat analysis.

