### **10.2. EFFICACY**

All subjects who receive study medication will be evaluated for efficacy.

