#### **10.2.1. Primary Efficacy**

Summary statistics will be determined for change in lesion volume by a radiologist blinded to the time of the MRI and whether the patient was on treatment or placebo. The initial MRI will be compared to the MRI after 20 week of sildenafil or placebo. If the subject on placebo elects to take sildenafil for 20 weeks the MRI used for comparison after 20 weeks of sildenafil will be the MRI taken after 20 weeks of placebo.

We will include in the interim analysis information about the characteristics of LMs. We will do a sub-analysis looking at specifics of location, lesion type (microcystic, macrocystic, or mixed and percent macrocystic), as well as previous procedures, infections or other interventions. If this process documents characteristics of lesions that do or do not respond to sildenafil, we will reconsider our study entry criteria and submit a protocol amendment for the IND and this grant, focusing more on specific characteristics of which type of lesion a subject should have in order to be enrolled in the trial.

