| Hearing exam                                  | x             |  |   |  |   |  |   | x                                       |   |
| Administer and dispense study medication      |                             | x  |   | x  |   | x  |   |   |   |
| Monitor vital signs every 30 mins for 2 hours |                             | x  |   |  |   |  |   |   |   |
| Collect unused study medication               |                             |  |   | x  |   | x  |   | x   |   |
| Dispense or review medication diary           |                             | x  |   | x  |   | x  |   | x   | x   |
| End of treatment                              |                             |  |   |  |   |  |   | x   |   |
| MRI   | x                           |  |   |  |   |  |   | x   |   |
| Review adverse events                         |                             | x  | x   | x  | x   | x  | x   | x   | x   |
| Unblind treatment                             |                             |  |   |  |   |  |   | x                                       |   |
| End of study/ Exit form                       |                             |  |   |  |   |  |   |   | x   |

 The "-A" suffix at end of Visit name indicates visits that are for the crossover Active Treatment Period, an option offered to any subject who received placebo during the Original Treatment Period.

 At Week 20, treatment will be unblinded and if subject received placebo then they have the option to enter the Active Treatment Period. Unblinding is performed only at the Week 20 Visit of the Original Treatment Period.

 If subject is female who has reached menarche.

 If hearing exam is not successful at screening, it will be repeated at subsequent visits until a satisfactory hearing test result is obtained.

 Subjects who exit early will not have a final MRI but we will attempt to obtain a Urine Pregnancy Test.

 Subjects local to a cooperating research site will attend Week 4, Week 12, and Week 32 visits at their cooperating site.

 Subjects local to a cooperating research site will be offered the option to have this procedure at their cooperating site or at Stanford.

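### Section 7.2 lets missed visits, procedures or doses end study participation, and early exits have no final MRI, so the primary outcome is lost for adherence-related reasons

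*Combined protocol and SAP*

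**What the plan says.** Section 7.2 defines discontinued subjects. Besides families who choose to stop, safety withdrawals and users of prohibited treatments, it includes those "who have missed a sufficient number of study visits, procedures or test medication doses as to be ineligible for further participation". It gives no count, proportion or period and does not say who decides. The compliance checks at Weeks 4, 12 and 20 (Sections 7.1.5 and 7.1.6) have no threshold. The discontinuation criteria mentioned in Section 7.1.5 are not accompanied by any adherence figure.

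The consequences are set elsewhere:

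- Section 7.1.13, Early Exit: "The subject will be exited from the study".
- Table 16-1, footnote 5: "Subjects who exit early will not have a final MRI but we will attempt to obtain a Urine Pregnancy Test".
- Section 7.2 itself: "All subjects who discontinue the study prior to completing the regularly scheduled visits must complete the EOT and Exit Visit procedures described in Section 7.1.11".

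The primary comparison needs the second scan. Section 10.2.1 says "The initial MRI will be compared to the MRI after 20 week of sildenafil or placebo". The analysis sets are broad: "All subjects who receive study medication will be evaluable for the intent-to-treat analysis" (Section 10.1) and "All subjects who receive study medication will be evaluated for efficacy" (Section 10.2).

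**The concern.** Voluntary withdrawal is a separate ground, so the missed-visit and missed-dose clause can reach a child whose family still wants to take part. The route from there is exit from the study, no second MRI and no primary outcome. The protocol itself creates this loss, and it depends on behaviour after randomisation.

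Missed doses are foreseeable. Dosing three times daily for 20 weeks is 3 × 7 × 20 = 420 doses, in children from six months of age. Families at cooperating sites must also travel to Stanford for Week 20. If side effects or lack of benefit drive the missed doses, the children removed will differ between arms. The children left with two scans would then lean towards those who tolerated the drug and took it, under a plan that calls the analysis intent-to-treat.

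**Working it through.** There is no plan figure to reproduce. Section 11 bases the sample size on availability and states no effect size, standard deviation, significance level, power or dropout rate. The main check is on the text; the arithmetic only gives scale.

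**1. The chain.** Section 7.2 (missed visits, procedures or doses end eligibility) → Section 7.1.13 (exit from the study) → Table 16-1 footnote 5 (no final MRI) → Section 10.2.1 (the outcome is the change between two MRIs). Section 7.1.5, item 4, also sends a child whose treatment is permanently stopped to Early Exit. The plan therefore has no category for a child who is off medication but still followed.

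**2. What the analysis has for a removed child.** Sections 10 and 11 name no method for a missing MRI. Section 7.4.3 mentions a linear mixed model for volume over time, in the text on tape measurement. The blinded period has only two scheduled MRIs, so a child without the second contributes a baseline scan and no observed change.

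**3. Counts.** Section 5.1 aims for 40 subjects with 20 weeks of therapy and an MRI, out of up to 60 enrolled. The synopsis expects 55 to start medication.

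- Gap from 60: 1 − 40/60 = 33.3%.
- Gap from 55: 1 − 40/55 = 27.3%.
- Placebo arm at 2:1: 60/3 = 20, 55/3 = 18.3, 40/3 = 13.3. One lost placebo outcome is 5%, 5.5% or 7.5% of that arm.

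The documents do not say how much of the gap would come from the missed-dose rule, so its share is anywhere from 0 to 20 of 60.

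**4. Precision.** My assumptions: two-sided 0.05, 80% power, 2:1 allocation, normal approximation, losses proportional across arms. With n_c the number on placebo, the detectable difference in SD units is (1.960 + 0.842) × √(1/n_c + 1/(2n_c)). For 60 analysed, n_c = 20 gives 2.802 × √0.075 = 0.767.

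| Analysed | Loss from 60 | Detectable difference (SD) | Power if true difference is 0.767 SD |
|---|---|---|---|
| 60 | 0% | 0.767 | 80.0% |
| 57 | 5% | 0.787 | 77.9% |
| 54 | 10% | 0.809 | 75.7% |
| 48 | 20% | 0.858 | 70.7% |
| 40 | 33% | 0.940 | 62.8% |

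This is loss of precision only and says nothing about bias.

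**5. Bias, as an extreme illustration.** Let the effect be D in sildenafil children who stay and 0 in the fraction p removed. Removed children supply no outcome, and placebo losses do not shift the placebo mean. The effect in the whole arm is (1 − p)D, and the estimate from those scanned is D. The ratio is 1/(1 − p): 1.05 at p = 0.05, 1.11 at p = 0.10, 1.25 at p = 0.20, and 1.00 if the rule removes nobody. The documents support no particular value of p.

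**The case against.** The strongest reply has five parts.

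- **Some of these children are already being lost.** Section 7.2 also requires three contact attempts, the last by registered mail, for families who persistently do not return. Keeping the child in the study on paper will not bring such a family to Stanford. This stands: the change recovers only those still willing to attend.
- **Exit procedures may recover the scan.** Sections 7.1.13 and 7.2 call for end-of-treatment procedures, and Table 16-1 puts an MRI at Week 20. But footnote 5 denies it to early exits, and Section 7.1.13 lets the family not return. Section 7.2 also points to 7.1.11 (Week 20 Active) rather than 7.1.13 (Early Exit). Even if a scan were done, it would be at exit and not at Week 20.
- **Blinding makes removal unlikely to differ by arm.** Blinding to Week 20 guards against removal based on knowledge of the allocation. It does not stop side effects or absence of benefit from affecting how doses are taken. Different removal rates by arm are possible, not shown.
- **Safety follow-up continues.** Adverse events are recorded at exit and unresolved ones are followed (Section 12.7). This stands, and I make no claim of a serious safety gap.
- **The study is exploratory.** Section 11 says so, yet it plans efficacy and futility looks at 15, 30 and 45 subjects, where a few missing outcomes carry most weight.

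Two stronger readings are tempting and should not be drawn. A reader might infer that Section 7.2 removes children from the intent-to-treat population. It does not: Sections 10.1 and 10.2 keep every dosed subject, and what is missing is the outcome. A reader might also see a contradiction with Section 6.2, "All subjects will have the option to receive 20 weeks of sildenafil in this open label extension study design", because a removed placebo child does not reach the open-label course. The synopsis makes that option conditional on completing 20 weeks of placebo, and Section 7.1.6 places the choice at the Week 20 visit, so there is no conflict.

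**Conclusion.** The point holds on the text. Followed as written, Section 7.2, Section 7.1.13 and footnote 5 together lose the primary outcome for children who miss visits, procedures or doses, while Sections 10.1 and 10.2 still count them. Setting a number would make the rule consistent but would still select on behaviour after randomisation.

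The size of the bias cannot be computed from the documents. The 5%, 11% and 25% figures rest on the assumption that removed sildenafil children would show no effect, and on removal rates I chose. They illustrate and do not estimate. The precision figures rest on assumed error rates and proportional loss, and the rule's share of that loss could be zero. The change is worth making because the loss is avoidable and the remedy is cheap.

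**What to change.** 1. Amend Section 7.2 so that missed visits, procedures or doses do not by themselves end study participation.
2. Separate stopping study medication from leaving follow-up, in Sections 7.1.5, 7.1.13 and 7.2. This takes no position on when medication should stop.
3. State that these children stay in follow-up through the scheduled Week 20 visit and MRI unless consent is withdrawn, and are analysed in their randomised arm.
4. Reconcile the end-of-treatment requirement in Sections 7.1.13 and 7.2, including the reference to 7.1.11, with footnote 5 to Table 16-1.
5. Describe adherence by arm from the medication journals and drug counts already collected.

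The cost is a few sentences of amendment and some extra follow-up effort; the MRI is already scheduled. The estimated effect may be slightly smaller because poor adherers stay in. Some families who have stopped attending will still be lost, so some MRIs will still be missing.

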### **7.3. SUBJECT PREGNANCY**

Females of child-bearing potential (defined as post-menarche as documented in the medical history) are not excluded from the study, though we do not expect to enroll sexually active females since the upper age limit is 10 years old. However, if a subject becomes pregnant during the study, the investigators should be contacted immediately and the medication should be stopped. Pregnancy is not reportable as an adverse event; however, complications related to the pregnancy may be reportable as determined on a case-by-case basis. Pregnancy-related information will be collected until termination of the pregnancy. The subject who becomes pregnant will be removed from the trial.

#### **7.3.1. Birth Control Measures**

Females of childbearing potential (those who are post-menarche as documented in the medical history) may participate in the study if they meet all of the following conditions:

- they are not breast feeding;
- they have a negative urine or serum pregnancy test at screening;
- they agree to undertake a urine pregnancy test at the completion of week 20 of treatment or placebo
- they agree to undertake a urine pregnancy test upon exiting the study if they elect to withdraw prior to the week 20 pregnancy test;
- they do not intend to become pregnant during the study;
- they are using adequate birth control methods and they agree to continue using those methods for the duration of the twenty (20) weeks of treatment or placebo.

Adequate birth control methods are defined as: hormonal—topical, oral, implantable or injectable contraceptives; mechanical—spermicide in conjunction with a barrier such as a condom or diaphragm; IUD; or, surgical sterilization of partner. For non-sexually active females, abstinence may be regarded as an adequate method of birth control; however, if the subject becomes sexually active during the study, she must agree to use an adequate birth control method as described above for the remainder of the study. Since the oldest age at entry for this trial is 10 years of age we expect all females who have completed menarche to not be sexually active but we will still discuss this topic during the visits in a sensitive way with the parent or guardian so that the child will not be embarrassed during the visit. We will discuss this topic with the child in accordance with the wishes of the parent or guardian.

## 7.4. STUDY METHODS AND MEASUREMENTS

### 7.4.1. Demographic information

General demographic data include age, sex, race, and ethnicity. Location of the lymphatic malformation, age at diagnosis, confirmatory diagnostic tests (previous MRIs, biopsies, etc), family history of lymphatic malformation, and associated complications, e.g., infection, disability.

### 7.4.2. Vital signs

Vital sign measurements include measurement of temperature (oral or tympanic membrane), resting pulse rate, respiration rate, oxygen saturation, systolic and diastolic blood pressure; along with height and weight.

### 7.4.3. Lymphatic malformation assessment

The most precise method of lymphatic malformation evaluation will be the MRI examination. Clinical assessment of each lymphatic malformation includes measuring the hemicircumference of the lesion by using a soft measuring tape placed on the skin over the area of the widest diameter of the lesion. The investigators will be fully trained in the standardized methods to obtain these measurements. We have found in our preliminary subjects that the investigators vary in their measurement of length, width and hemispheric measurement unless they practice these measurements together in order to standardize their methods. The length, and width, will then be calculated as described in Figure 2 of Berk et al.(Berk, Berk et al. 2011) We will use linear mixed model to compare the changes in volume over time between and within subjects who receive placebo and those who receive sildenafil. In order to document the site of the measurements a diagram will be drawn by hand or photographs will be taken of the methods. Each clinic visit will try to duplicate the measurements methods used in the initial visit.

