covered in this IND application. That IRB trial would allow up to five years follow up on subjects and would only allow investigators to observe how the subject is doing long term, whichever treatment options the subject pursues in consultation with their regular doctor in that time. That planned follow up protocol will allow Stanford to contact the subjects several times a year in order obtain information about any therapy they may elect to follow, including sildenafil if their regular doctor prescribes it, and their response to any therapy.

Multi-Center:

Yes

Number of Centers:

Up to 4

Blinding:

|                |     |
|----------------|-----|
| Observer-Blind | Yes |
| Subject-Blind  | Yes |
| Double-Blind   | Yes |

Randomization:

Group Assignment Ratio: 2:1 randomization of two subjects who receive sildenafil to one subject who receives placebo.

Concurrent Control:

No other treatments for lymphatic malformation will be allowed except antibiotics and/or surgical drainage if the lesions become infected. Treatment for recurrent infections in the lymphatic malformation will be allowed and documented during the trial. Concurrent medications will be documented. Subjects who require sclerosing agents or excisional surgery of their lymphatic malformation will be withdrawn from the trial.

Variable(s): PRIMARY: Change in lesion volume over twenty weeks of the test medication as evaluated by MRI examination. Comparison of placebo to sildenafil treated subjects.

SECONDARY: Change in lesion volume estimated using a soft tape measure to measure the length, width, and hemispheric measurement of each of the lymphatic malformations. (Berk, Berk et al. 2011) Completion of the form *Lymphatic Malformation Measurements*.

Subject's evaluation of the change in lesion clinical characteristics from baseline to 20 weeks by examining decreased discomfort, texture or thickness, distortion of normal anatomy or overall change obtained in the subject's

completion of *Subject's Assessment of Lymphatic Malformation Change* form.

Physician's evaluation of the lesion clinical characteristics on the day of the visit. This includes color, tenseness and texture, superficial component, deep component, and distortion of anatomical landmarks. This requires completion of the *Lymphatic Malformation Assessment* form for each LM site.

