### 7.1.2. Visit 1 – Screening Visit [usually Day -7 to -1] at Stanford

NOTE: Any subject for whom an informed consent/assent has been obtained, but fails to meet the required entry criteria is considered to be a screen failure. All demographic information must be captured with the reason for screen failure specified.

1. Explain the purpose and nature of the study, and have the subject's parent or legally authorized representative, read, sign, and date the IRB-approved informed consent document. Even subjects who may have signed a consent form at the cooperating research study site prior to laboratory, eye and hearing exams will sign the Stanford consent form at this visit. The subject's assent to participate in the study will be obtained if the subject is between 7 and 10 years of age. The informed consent document must be signed and dated by the individual who consents the subject. A photocopy of the signed informed consent document will be provided to the parent or legally authorized representative. A copy of the informed consent will also be placed in the subject's medical record. The original copy will be maintained in the research files.

----- Do not proceed until consent has been obtained -----

2. Screen the subject against protocol inclusion and exclusion criteria (Sections 5.2, 5.3). Subjects not meeting the criteria are screen failures and must exit the study at this point.
3. Obtain demographic information and medical history, including information on all medications currently being taken at the time of signing the informed consent. Instruct the subject and/or caregiver of the excluded medications and give them a list. Document previous treatments for the lymphatic malformation and previous infections in the lymphatic malformation.
4. Review the subject's previously obtained MRI, X-rays or CT scans and other laboratory test results with the subject.
5. Perform a physical examination including heart and pulmonary auscultation, liver and spleen palpation, abdominal auscultation and palpation, and documentation of peripheral pulses. Examine the characteristics of their lymphatic malformation to see that it meets the criteria for the trial.
6. Obtain Vital Signs including height, weight, temperature, heart rate, blood pressure, respiratory rate, and oxygen saturation.

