#### **7.1.3. Baseline Study [Day 0 (medication dispensed)] at Stanford**

This will usually be the day after the screening.

1. Review inclusion and exclusion criteria with the subject, including the results of their laboratory data, eye examination, and MRI. If subject no longer meets criteria for participation, exit the subject from the study as a screen failure.
2. Obtain demographic information and medical history, including information on all medications currently being taken. Document concomitant medications. Instruct the subject and/or caregiver of the excluded medications and give them a list if they do not have their list that was previously given to them.
3. Perform a physical examination including heart and pulmonary auscultation, liver and spleen palpation, abdominal auscultation and palpation, and documentation of

peripheral pulses. Examine and describe the characteristics of their lymphatic malformation to see that it meets the criteria for the trial.

4. Obtain Vital Signs including height, weight, temperature, heart rate, blood pressure, respiratory rate, and oxygen saturation.
5. Clinical assessment of each lymphatic malformation including measuring the hemicircumference of the lesion by using a soft measuring tape placed on the skin over the area of the widest diameter of the lesion. The length, and width, will then be calculated as described in Figure 2 of Berk et al.(Berk, Berk et al. 2011) In order to document the site of the measurements a diagram will be drawn by hand or photographs will be taken of the methods. Each clinic visit will try to duplicate the measurements methods used in the initial visit.
6. Physician's evaluation of the lesion clinical characteristics on the day of the visit. This includes color, tenseness and texture, superficial component, deep component, and distortion of anatomical landmarks. This requires completion of the *Lymphatic Malformation Assessment* form for each LM site.
7. Site investigator will acquire digital photographs of each lymphatic malformation as described in Section 7.4.4, and summarized as follows:
  - Subject will be seated on a chair. If subject is an infant, then subject's parent or guardian will be seated on a chair with subject sitting on his/her knees or in his/her arms.
  - All photographs will include a color chart in the field of view, held in the same plane as the target lymphatic malformation.

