#### **10.2.2. Secondary Efficacy**

The secondary efficacy variables will be change from baseline and at visits four weeks twelve weeks, twenty weeks and 32 weeks.

These will include the changes in the soft tape measurements of the lesion by comparing the measurements of length, width, and hemispheric measurement. The volume of the lymphatic malformation will be estimated based on these measurements.

Statistical analysis of the *Subject's Assessment of Lymphatic Malformation Change* form. This will give data on the subject's evaluation of the change in lesion clinical characteristics from baseline, such as decreased discomfort, texture or thickness, distortion of normal anatomy or overall change by correlating the data obtained in the subject's completion of *Subject's Assessment of Lymphatic Malformation Change* form.

Statistical analysis of the *Lymphatic Malformation Assessment* form for each LM site. This will give data on the physician's evaluation of the lesion clinical characteristics on the days of the visits. This includes color, tenseness and texture, superficial component, deep component, and distortion of anatomical landmarks.

Statistical analysis of the *Lymphatic Malformation Assessment of Change* form for each LM site. This will give data on the physician's evaluation of the change in lesion clinical characteristics from baseline, such as change in texture or thickness, change in distortion of normal anatomy, and over change in lesions.

Change in LM volume from MRI assessments in relation to BSA will also be carried out. REDCap calculates the BSA from height and weight measurements at each visit. Since growth can be non-linear, relating the LM volume to a subject's BSA may help to explain why a small change to the LM (by MRI volume analysis) is assessed as moderate by the investigator and parents of the subject (i.e., the LM may have stayed the same size but the child grew quickly, so the LM appears smaller by visual assessment).

The digital photographs of each lymphatic malformation in this study will be acquired by the site investigators. At least two digital photographs of the lymphatic malformation will be acquired for each patient at each scheduled study visit, a front-on view and a side-on view. See Section 7.4.4. The clinical photographs evaluated by blinded observers in a blinded manner by physicians not associate with this trial. The observers of the

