## 16. STUDY PLAN

Table 16-1: Study Procedures by Treatment Day

| Visit:  | Screening
(Day -7 to +1) | Baseline &
Baseline-A 
(Day 0) | Week 2 &
Week 2-A 
(~4 1 Day) | Week 4  &
Week 4-A 
(~4 14 Days) | Week 8 &
Week 8-A 
(~4 1 Day) | Week 12  &
Week 12-A 
(~4 14 Days) | Week 16 &
Week 16-A 
(~4 1 Day) | Week 20 &
Week 20-A 
(~4 14 Days) | End of Study 
Early Exit 
(Week 32)
(~4 14 Days) |
|---|-----------------------------|--|---|--|---|--|---|---|---|
| Procedures:                            |                             |  |   |  |   |  |   |   |   |
| Informed Consent/Accent                       | x                           |  |   |  |   |  |   |   |   |
| Inclusion/Exclusion criteria                  | x                           |  |   |  |   |  |   |   |   |
| Vital signs (height, weight, HR, BP, temp)    | x                           | x  |   | x  |   | x  |   | x   | x   |
| Complete history                              | x                           |  |   |  |   |  |   |   |   |
| Interval history                              |                             | x  | x   | x  | x   | x  | x   | x   | x   |
| Physical examination                          | x                           | x  |   | x  |   | x  |   | x   | x   |
| Phone call                                    |                             |  | x   |  | x   |  | x   |   |   |
| Assessment of LM by MD                        | x                           | x  |   | x  |   | x  |   | x   | x   |
| Assessment of LM by participant               |                             |  |   | x  |   | x  |   | x   | x   |
| LM measurements                               | x                           | x  |   | x  |   | x  |   | x   | x   |
| LM photographs                                | x                           | x  |   | x  |   | x  |   | x   | x   |
| Laboratory tests                              | x               |  |   |  |   |  |   | x   |   |
| Urine pregnancy test                          | x               |  |   |  |   |  |   | x                                       |   |
| Ophthalmology exam                            | x               |  |   |  |   |  |   | x                                       |   |

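### Table 16-1 schedules two pre-dose tape measurements, but the visit text omits one and the analysis does not say how it is used

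*Combined protocol and SAP*

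**What the plan says.** Tape volume is a secondary endpoint. The synopsis (section 2) lists "SECONDARY: Change in lesion volume estimated using a soft tape measure", and the primary variable is MRI volume.

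In Table 16-1 (section 16) the row "LM measurements" is marked at Screening, Baseline, Weeks 4, 12 and 20, and End of Study. The synopsis gives the tape-measurement form the same name, so the row refers to the tape.

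The visit text differs. Section 7.1.2 (Screening) asks only for an examination: "Examine the characteristics of their lymphatic malformation to see that it meets the criteria for the trial". None of its seven steps is a tape measurement. The first one in the text is step 5 of section 7.1.3, on Day 0: "Clinical assessment of each lymphatic malformation including measuring the hemicircumference of the lesion by using a soft measuring tape". Of the gap between the two visits, section 7.1.3 says: "This will usually be the day after the screening". Both visits are at Stanford and both come before the first dose.

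On analysis, section 10.2.2 says: "The secondary efficacy variables will be change from baseline and at visits four weeks twelve weeks, twenty weeks and 32 weeks". Section 7.4.3 adds: "We will use linear mixed model to compare the changes in volume over time between and within subjects". Neither section defines the tape baseline or gives the Screening value a use.

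On error, section 7.4.3 says: "We have found in our preliminary subjects that the investigators vary in their measurement of length, width and hemispheric measurement". The same sentence exempts investigators who have practised jointly, and full training is planned. No SD, coefficient of variation, intraclass correlation or repeatability figure appears.

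**The concern.** The table and the text disagree on whether a second pre-dose reading exists. Staff who follow section 7.1.2 will not take it. Staff who follow Table 16-1 will take a reading that has no stated purpose. Later visits are also told to repeat the technique of the initial visit, and the two sources disagree on which visit first sets that technique.

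Error in the baseline value enters every later change score. MRI is scheduled only at Screening and at the end of each treatment period, so tape is the only volume measure at Weeks 4, 12 and 32. Sample size is set by availability (section 11), so precision from data already scheduled is worth having. Two readings a day apart, with negligible true change between them, would also give the repeatability figure that the protocol lacks.

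The choice of baseline should be fixed in advance, because each subject is unblinded at Week 20 and looks at the data are planned after 15, 30 and 45 subjects.

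**Working it through.** **Inputs.** From the documents: two pre-dose tape measurements (Table 16-1), usually one day apart (section 7.1.3). No variance, correlation or power calculation is given, so there is no plan figure to reproduce. All correlations and variance ratios below are assumptions.

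**Notation.** Each reading has variance 1. *r* is the correlation of a pre-dose reading with Week 20, and *b* is the correlation between Screening and Day 0.

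**1. Change score.** The variance with one baseline is 2 − 2*r*. With the mean of two it is 1 + (1 + *b*)/2 − 2*r*. The relative reduction is (1 − *b*)/[4(1 − *r*)].

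**2. Baseline-adjusted analysis.** The residual variance is 1 − *r*² with one baseline and 1 − 2*r*²/(1 + *b*) with the mean of two.

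**3. Equal correlations (*b* = *r*).**
- Change score: 2(1 − *r*) becomes 1.5(1 − *r*), a 25% reduction at every *r*. This is the ceiling whenever *b* is at least *r*.
- Adjusted, for *r* = 0.5, 0.6, 0.7, 0.8, 0.9: reductions of 11%, 14%, 17%, 20%, 22%. For example, at *r* = 0.8, 0.36 becomes 1 − 1.28/1.8 = 0.289, and 1 − 0.289/0.36 = 20%.

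**4. Next-day correlation above the 20-week correlation.** This is the more plausible pattern in a treatment trial.

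| *b* | *r* | Change score | Reduction | Adjusted | Reduction |
|---|---|---|---|---|---|
| 0.90 | 0.80 | 0.400 to 0.350 | 12.5% | 0.360 to 0.326 | 9% |
| 0.95 | 0.80 | 0.400 to 0.375 | 6% | 0.360 to 0.344 | 5% |
| 0.90 | 0.50 | 1.000 to 0.950 | 5% | 0.750 to 0.737 | 2% |

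**5. The same question in error components.** Let *e* be the error variance, *d* the variance of true change, and *s* the share of pre-dose error common to both visits. The change-score variance goes from 2*e* + *d* to *e* + *e*(1 + *s*)/2 + *d*. The reduction is 0.5(1 − *s*)/(2 + *d*/*e*).
- *s* = 0 and *d*/*e* = 0, 0.5, 1, 2, 4: reductions of 25%, 20%, 17%, 12.5%, 8%.
- *d* = 0 and *s* = 0.2, 0.5, 0.8: reductions of 20%, 12.5%, 5%.
- *s* = 1: no reduction.

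**6. On the standard-error scale.** A 25% cut in variance multiplies the standard error by √0.75 = 0.866. A 2% cut multiplies it by √0.98 = 0.990. The standard error therefore falls by about 1% to 13%.

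**The case against.** The strongest reply is that the plan already names the error and its remedy. The variation in section 7.4.3 is between investigators who have not standardised their technique together, and training is promised. If one Stanford observer takes both pre-dose readings, that observer's error is common to both and averaging leaves it in place (step 5). Subjects from other sites are measured locally at Weeks 4, 12 and 32, probably by other observers, and nothing done at baseline removes that component. A single Day 0 baseline is also valid and unbiased, the endpoint is secondary, and section 11 calls the study exploratory and descriptive.

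Most of this stands, and it limits the size of the gain. It does not remove the mismatch between Table 16-1 and section 7.1.2 or supply the missing baseline definition. Training may shrink the error but is not shown to eliminate it. If any of the error is independent between the two readings, using both lowers the variance.

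A reader might go further and infer that the plan discards the Screening value and takes change from one noisy reading. The documents do not say so. Baseline is undefined, and the mixed model in section 7.4.3 could take both values. Use of Day 0 alone is the natural reading, not a stated rule.

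**Conclusion.** The point holds as a minor one about a secondary endpoint. Two pre-dose tape measurements are scheduled, the visit text omits one, and no section says how it enters the analysis. Using both would lower the variance of the tape-volume change by about 2% to 25% over the scenarios tested. The gain tends to zero if the two readings share all their error.

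A reader might infer a firm saving of about one fifth, worth 20% to 29% more subjects. Those figures come from setting the next-day and 20-week correlations equal at 0.7 to 0.9 in the adjusted analysis (0.51/0.4235 = 1.20 and 0.19/0.1474 = 1.29). The documents support neither that equality nor those values. With the next-day correlation higher, as in step 4, the reduction is about 2% to 12.5%.

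The primary MRI comparison is untouched. Between-observer error at local-site visits also remains, so the pair of readings would show repeatability at Stanford and not the full error in later change scores.

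**What to change.** - Reconcile section 7.1.2 with Table 16-1 so that the Screening tape measurement is listed and taken.
- In sections 10.2.2 and 7.4.3, state that the randomised-period tape analysis uses both pre-dose values: either both as pre-dose observations in the linear mixed model, or their mean as the baseline. Limit this to the randomised period, since Table 16-1 has no second screening measurement before the open-label baseline.
- Report the within-subject SD of the pair, √(mean squared difference / 2), and note whether the same observer took both readings.
- If a precision gain is quoted, give it as a range with its assumptions.

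The cost is one brief tape measurement at Screening, already in the study table, and minor wording. It is not strictly free, because a site that follows section 7.1.2 does not take that measurement now.
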